#### Statistical Analysis:

The primary endpoint in the phase 2 part is the proportion of subjects who achieve a response (R) between the Week 1 and Week 7. Based on data observed in this study and external information available, the sponsor will make following decisions based on the totality of information at the interim analysis at the end of Week 7 in the phase 2 part:

- whether to proceed to the phase 3 part;
- select a dose to befurther studied in the phase 3 part.

Whether to proceed to the phase 3 part will be based on the Go/No-Go decision framework. If at least one dose shows a high likelihood that the target efficacy can be achieved and the safety of this dose is acceptable, the phase 3 part will start. On the other hand, if the efficacy of both doses is shown to be unlikely to be clinically significant, the trial will be terminated and Phase 3 will not be initiated. If the analysis results do not meet any of the two situations above, the subjects will continue to be observed or sample size will be increased to collect more long-term efficacy data to decide whether to enter Phase 3. The dose selection for the Phase 3 will be based on the comparisons of the efficacy, safety and biomarkers between the two doses.

The primary efficacy endpoint in the Phase 2 is set primarily to verify the mechanism of action of the drug. Since the primary efficacy endpoint in the Phase 2 is for short-term efficacy assessment and the primary efficacy endpoint in the Phase 3 is for long-term efficacy assessment, the decision for Phase 3 will consider not only the observed short-term efficacy as measured by the Phase 2 primary efficacy endpoint, but also the long-term efficacy observed in subjects who have partially completed the trial, the predictions of

the long-term efficacy and the duration of efficacy based on the biomarkers, the efficacy and safety of the competitive products, and the safety data observed from this trial.

The primary endpoint of the Phase 3 is the proportion of subjects with a platelet count  $\ge 30 \times 10^{9}$ /L at  $\ge 4$  of 6 visits from Week 19 to 24 and the platelet count is at least twice baseline level, without bleeding events or rescue treatment. The statistical tests for differences in response rates between groups will be performed based on a normal approximation of the binomial distribution without continuity correction.

The hierarchical testing will be used to analyze the secondary endpoints in the Phase 3 trial. If the statistical test of the primary efficacy endpoint is statistically significant, other efficacy measures between the treatment groups will continue to be tested. The secondary endpoints will be ranked tentatively as the response rate within 7 weeks, the response rate within 24 weeks, the complete response (CR) rate within 24 weeks, and the complete response (CR) rate within 7 weeks.

An independent data monitoring committee (DMC) will be established prior to the enrollment of the first subject to periodically review the safety data for ensuring the safety of the subjects. The data monitoring committee will be responsible for the planned interim analysis, interpretation of the results, and the recommendations for action according to the protocol. To ensure the credibility of the trial, the sponsor will not be involved in the operation of this independent data monitoring committee. The persons involved in the trial, including all the sponsor employees, and the third-party personnel and investigators related to the trial, cannot be the members of the data monitoring committee.

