# Main Inclusion and Exclusion Criteria (for both phase 2 and phase 3 parts):

#### Inclusion Criteria:

- 1. Signed written informed consent.
- 2.  $\geq$  18 years of age at the screening visit, male or female.

3. Female patients will be eligible to participate if meeting the criteria below:

a. Non-childbearing potential (i.e., physiologically incapable of pregnancy, including women who have been menopausal for 2 years)

b. Women of child-bearing potential (WOCBP) must have a negative serum pregnancy test at the first visit, and agreed to correctly use one of the following acceptable and effective methods of contraception (i.e., following the approved product label and physician's instructions) throughout the study from the start of study visit (Screening) until 90 days after the last dose:

- Complete abstinence (when consistent with the patient's preference and previous lifestyle); or
- Levonorgestrel implant should be implanted at least 1 month ahead of study drug administration, but implant time cannot be more than 3 years; or
- Progesterone should be injected at least 1 month ahead of that study drug administration; or
- Oral birth control pills (combination contraceptives or progestins only) administered for at least 1 month prior to study drug administration; or
- Dual birth control: condom or cervical cap (diaphragm or cervical cap) with spermicide (foam/gel/cream/suppository); or
- Intra-uterine devices (published data showing an estimated maximum failure rate is less than 1% per year), implanted by qualified physicians; or
- Estrogen vaginal ring; or
- Transcutaneous contraceptive patch.
- 4. Male patients must use effective contraception methods or their heterosexual partners must use effective birth control during their participation in this clinical trial.
- 5. Diagnosis criteria: meet the American Society of Hematology 2011 diagnosis criteria for persistent or chronic ITP. The average number for platelet count at the screening visit and predose platelet count on the day of first dose (at least 1 day apart) is < 30 × 10 /L, and platelet count is not > 35 × 10 /L for any of two tests. No severe bleeding occurs within 4 weeks prior to the screening visit.
- 6. Patients who have received and failed (poor response, or unmaintained response, or relapse) at least 1 first line of ITP therapy (glucocorticoids and/or intravenous gamma globulin), or who are contraindicated, intolerable, or refuse standard therapy.

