- 7. This study allows concomitant drugs for the treatment of ITP, detailed requirements are as follows:
  - Glucocorticoids: prednisone or other equivalents ≤ 20 mg/day are allowed within at least 2 weeks prior to the first dose of the study drug, with dose unchanged or regularly reduced;
  - Danazol: The dose remained unchanged within 3 months prior to the first dose of study drug or has been discontinued for at least 2 weeks prior to the first dose of study drug;
  - Immunosuppressants (azathioprine, cyclosporine A, mycophenolate mofetil only): The dose remains unchanged within 3 months prior to the first dose of the

study drug, or has been discontinued for at least 2 weeks prior to the first dose of the study drug;

- Eltrombopag: The dose remained unchanged within 4 weeks prior to the first dose of the study drug or has been discontinued for at least 2 weeks prior to the first dose of the study drug.
- 8. Willing and be able to receive treatment and complete appropriate assessments as required by the protocol, at the discretion of the investigator.
- 9. Clinical laboratory results at screening must be acceptable to the investigator.

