# STUDY SCHEDULE

Study Phase	Screenin g Phase	Т	reatme	ent Pha	ase				Follo	w-up F	hase i				Early Withdraw al Visit b	
Visit Number															ET	
Weeks																
Days																
Visit Window (days)																
Informed Consent																
Demographic Information																
Disease and Treatment History																
Concomitant Treatment Collection																
Vital Signs (temperature, blood pressure, pulse)																
Complete Physical Examination																
Key Physical Examination																
12-lead Electrocardiogram		Xm														
Hematology																
Blood Biochemistry		Xm														
Coagulation																
Viral Serology																
Hepatitis B Virus DNA e		Xm														
Mycobacterium Tuberculosis Test f																
Urine Analysis		Xm														
Serum Globulin, Albumin		Xm														
Pregnancy Test g																

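### The Phase 3 primary test is valid but unadjusted: using baseline platelet count and background ITP drug use as covariates could cut variance by about 0–10%, at almost no cost

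*Combined protocol and SAP*

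**What the plan says.** All references are to the combined protocol and SAP.

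- **Test.** Under Statistical Analysis, the between-group tests of response rates "will be performed based on a normal approximation of the binomial distribution without continuity correction". No covariate, stratum or stratified test is named for Phase 3. The Study Population section mentions balancing by the randomisation system, but only for Phase 2 and without factors.
- **Endpoint.** Response in Phase 3 requires, at 4 or more of the 6 visits in Weeks 19–24, a count of at least 30 × 10⁹/L, and "the platelet count is at least twice baseline level, without bleeding events or rescue treatment".
- **Baseline platelets.** Inclusion criterion 5 uses "The average number for platelet count at the screening visit and predose platelet count on the day of first dose": the mean must be below 30 and neither count above 35.
- **Background drugs.** Inclusion criterion 7 states: "This study allows concomitant drugs for the treatment of ITP". Continuing danazol, immunosuppressants and eltrombopag must be at a constant dose, for example "Eltrombopag: The dose remained unchanged within 4 weeks prior to the first dose of the study drug". Glucocorticoids may be given "with dose unchanged or regularly reduced". The Study Schedule has a row for "Concomitant Treatment Collection".
- **Secondary endpoints.** A tentative hierarchy of response rates ends with "and the complete response (CR) rate within 7 weeks".

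**The concern.** Each subject's response threshold depends on a known pre-treatment value. It is max(30, 2 × baseline): 30 for a baseline of 15 or less, rising towards 60 as a baseline defined as the mean of the two entry counts nears its limit. The comparison between arms ignores this value. It also ignores whether the subject is on other ITP treatment, which may affect counts at Weeks 19–24.

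Only efficiency is at stake. The type I error of the crude test already allows for chance imbalance in these variables. A standardised risk difference estimates the same marginal quantity, so the estimand does not change. If the covariates are prognostic, the confidence interval narrows; if not, almost nothing is lost.

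**Working it through.** **1. The planned sample size.** The plan gives 230 (115 per arm) but, in the supplied text, no alpha, power, response rates or dropout, so the figure cannot be reproduced uniquely. Per arm, n = [1.96·√(2p̄(1−p̄)) + z₁₋β·√(p₀(1−p₀)+p₁(1−p₁))]² / (p₁−p₀)², with two-sided 0.05 assumed. Several assumed sets land on or near 230:

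- 10% v 25%, 85% power, no dropout: (1.053 + 0.546)² / 0.0225 = 113.7, so 114 per arm, 228 in total.
- 15% v 35%, 90% power, 15% dropout: 97 / 0.85 = 114.1, so 115 per arm, 230 in total.
- 10% v 25%, 80% power, 10% dropout: 100 / 0.9 = 111.1, so 112 per arm, 224 in total.

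**2. Validity of the crude test.** Exact binomial enumeration at 115 per arm, common rates 2–40%, nominal two-sided 0.05, gives a size of 0.043–0.052 (pooled variance) or 0.043–0.053 (unpooled).

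**3. Large-sample gain.** With m₀, m₁ the covariate-specific response probabilities:

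- crude: n·Var = p₀(1−p₀) + p₁(1−p₁)
- adjusted: n·Var = E[m₀(1−m₀)] + E[m₁(1−m₁)] + Var(m₁−m₀)/2
- reduction = 1 − adjusted/crude

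Assumptions: 50% on a background drug, baseline uniform and independent of drug use.

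| OR drug use | OR per SD baseline | 5 v 20% | 10 v 30% | 15 v 35% | 20 v 50% |
|---|---|---|---|---|---|
| 1 | 1 | 0% | 0% | 0% | 0% |
| 1.5 | 1.5 | 2.1% | 2.9% | 3.5% | 3.9% |
| 2 | 2 | 5.6% | 7.8% | 9.1% | 10.3% |
| 3 | 2 | 7.1% | 9.8% | 11.4% | 12.7% |

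**4. Simulation of the endpoint, 115 per arm.** All inputs other than the entry rule and endpoint are assumed.

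- True log count: mean log 16, SD 0.5. Two entry counts with within-subject SD 0.3, with the limits of inclusion criterion 5 applied.
- Follow-up: between-subject change SD 0.4–0.6, common drift 0 or 0.3, treatment shift 0.36–0.46 on the log scale.
- Run with and without about 19% bleeding or rescue failures; 25–50% on a background drug.

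Results as the variance ratio, adjusted/crude:

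- Post-baseline drug shift −0.2 (taper) to +0.3, 28 scenarios: 0.935–1.005.
- Baseline platelets alone: 0.960–1.001.
- Drug shift +0.5, 2 scenarios: 0.877–0.906. This is hard to square with stable dosing and a mean count below 30 at entry.
- One-sided null rejection (nominal 0.025, Monte Carlo SE 0.0025): adjusted 0.024–0.028, crude 0.019–0.027.

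A separate simulation at 115 per arm gave ratios of 1.002 to 0.91 for shifts of −0.2 to +0.3 and 0.87 at +0.5. It showed no bias, and null rejection of 0.030 adjusted and 0.027 crude.

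**5. What this is worth.** Equivalent N = 230 × (1 − r); the standard error falls by 1 − √(1 − r).

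| Variance reduction r | Equivalent N | SE reduction | Power, 10 v 25% | Power, 15 v 30% | Power, 15 v 35% |
|---|---|---|---|---|---|
| 0 | 230 | 0% | 85.4% | 78.1% | 94.4% |
| 2% | 225 | 1.0% | 86.1% | 78.9% | 94.8% |
| 5% | 219 | 2.5% | 87.2% | 80.2% | 95.3% |
| 10% | 207 | 5.1% | 88.9% | 82.3% | 96.2% |

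**6. Sparse secondary endpoints.** The probability of no complete response among 115 placebo subjects is (1 − p)¹¹⁵. For assumed true rates of 0.5%, 1%, 2% and 3% it is 56%, 31%, 10% and 3%. A logistic model then separates, so a fallback is needed.

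**The case against.** **No error is shown.** The crude test is valid, transparent and conventional, and the benefit of replacing it may be zero. This stands, and is why the point is a suggestion only.

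**The text is a summary.** Covariates or strata may be specified in a fuller document. This also stands: the point concerns the supplied text alone. If randomisation is stratified on either factor, the unadjusted test would be somewhat conservative and the case for adjustment stronger.

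**Baseline is not wholly unused.** It is part of the response definition. That is correct; it is unused only in the comparison between arms. The supplied text also does not say which count is baseline. If it were the predose count alone, which may reach 35, the threshold could reach 70 rather than just under 60.

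**The size is assumed, and 10% may be too high.** The 28 scenarios with drug shifts up to +0.3 stop at 6.5%. Stable dosing before entry means much of a drug's effect is already in the baseline count. However, the separate simulation reached about 9% over the same shifts, and odds ratios of 2 give 6–10%. About 0–10% is therefore a fair range, with the upper end needing fairly strong covariates.

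**Power gains partly reflect size.** In the first simulation the crude test was sometimes conservative. Near 80% power, moving one-sided size from 0.0215 to 0.025 alone adds roughly 1.8 points, more than the largest simulated gain of 1.4 points for shifts up to +0.3. This stands; the variance ratios are the measure to rely on.

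**The yes/no drug indicator is crude.** It pools tapering steroids with stable drugs, whose effects may cancel. This stands as a limit on the gain.

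**Conclusion.** The point holds as an efficiency suggestion, with medium confidence. The planned Phase 3 test controls type I error and need not be called wrong. Adjusting for baseline platelet count and background ITP medication would reduce the variance of the same risk difference by about 0–10%, equivalent to 0 to 23 of 230 subjects. In a few simulated scenarios it gave no gain or a trivial loss (ratio up to 1.005, power −0.2 points). The range rests on assumed prognostic strength, response rates and drug use, none of which the documents give. Null rejection of the adjusted test was 0.024–0.030 across the simulations, close to nominal.

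**What to change.** Before unblinding, specify in the SAP:

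1. **Primary analysis.** A marginal risk difference from a logistic model with treatment, log baseline platelet count, baseline ITP medication (yes/no) and any randomisation strata, standardised over all randomised subjects, with a robust or influence-function standard error. State which count or mean of counts is baseline.
2. **Sensitivity analysis.** The planned unadjusted z-test.
3. **Secondary hierarchy.** The same method where events suffice. Fall back to the planned unadjusted test if the model fails to converge or separates, for example with no event in one arm.

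The Phase 2 part records the same Week 19–24 endpoint as a secondary endpoint and can give a rough look at prognostic strength, although 36 subjects are few.

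The cost is some SAP text and a few lines of code. Sample size and data collection are unchanged. The drawback is a less simple primary analysis, with little or no return if the covariates prove non-prognostic.

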#### Population Pharmacokinetics and Dose-Response Analysis:

All HBM9161 plasma concentration data obtained in this study will be used for the PopPK analysis (using a nonlinear mixed effects modeling [NONMEM]) to establish a PK model to characterize the PK of subcutaneous injection of HBM9161. The individual subject exposure parameters will be estimated based on the parameters estimated by the final PK model established for the further dose-response (exposure-response) analyses, including the exploratory analysis of correlation of PK/efficacy and PK/safety. The results of these analyses will be reported separately.

# STUDY SCHEDULE

Study Phase	Screenin g Phase	Т	reatme	ent Pha	ase				Follo	w-up F	hase i				Early Withdraw al Visit b	
Visit Number															ET	
Weeks																
Days																
Visit Window (days)																
Informed Consent																
Demographic Information																
Disease and Treatment History																
Concomitant Treatment Collection																
Vital Signs (temperature, blood pressure, pulse)																
Complete Physical Examination																
Key Physical Examination																
12-lead Electrocardiogram		Xm														
Hematology																
Blood Biochemistry		Xm														
Coagulation																
Viral Serology																
Hepatitis B Virus DNA e		Xm														
Mycobacterium Tuberculosis Test f																
Urine Analysis		Xm														
Serum Globulin, Albumin		Xm														
Pregnancy Test g																

## (continued)

Study Phase	Screen ing Phase	Tr	reatme	nt Pha	ase				Follo	w-up P	hase i				Early Withdraw al Visit b
Visit Number															ET
Weeks															
Days															
Visit Window (days)															
Review of Inclusion/Exclusion Criteria															
Subject Randomization															
Study Drug Administration															
Injection Site Assessment															Xp
Dispensing/Return of Subject Diary h															
Review of Subject Diary															
Adverse Event Collection															
WHO Bleeding Score															
Anti-HBM9161 Antibody Test i															
Immunoglobulins (IgG, IgM, IgA)												 		 	
Platelet Autoantibodies j															
PK Blood Sample Collection k															

Note:

a. Date of first dose of HBM9161 injection.

b. If the subject withdraws from the study early, the withdrawal visit should be completed within 2 days of the decision to withdraw from the study; if the subject withdraws in the middle of the treatment period, please observe the injection site reaction at the withdrawal visit until the reaction disappears.

c. The complete physical examination should be performed at the Screening Visit, Visit 6 (Week 4), Visit 9 (Week 7), Visit 20 (Week 24), and the Early Withdrawal Visit (Includes cardiovascular, respiratory, gastrointestinal, skin, neurological, and musculoskeletal systems, as well as head, eyes, ears, mouth, nose, throat, neck, lymph nodes and edema). Height and weight will be measured and recorded at the screening visit. Key physical examinations (including skin, mucosa and organ hemorrhage and edema) may be performed at other visits.

d. Viral serology test should be performed at screening, including HIV, HBsAg, HBcAb and HCV antibody. The HBV-DNA testing should also be performed in the subjects with HBsAg-negative but HBcAb-positive, and the subjects with clinically significant elevations in HBV-DNA are excluded.

e. The HBV-DNA testing is only performed in the subjects with HBsAg negative but HBcAb positive. The subjects with clinically significant elevations in HBV-DNA should be considered for the addition of the anti-HBV drugs according to the relevant guidelines.

f. The subjects with the known tuberculosis infection, a high risk of tuberculosis infection, latent tuberculosis infection or a history of tuberculosis infection should be excluded. Other subjects should have a tuberculin test or interferon gamma release assay to rule out the active TB infection.

g. All the female subjects of childbearing potential should complete the blood human chorionic gonadotropin (HCG) pregnancy test at screening. The serum or urine pregnancy tests may be done at the subsequent visits.

h. The subject diary helps the subjects record the medications and the adverse event across the visits.

i. The ADA analysis will be performed under the control of the sponsor. The serum samples will be tested for anti-HBM 9161 antibodies using the currently approved bioanalytical methods. The raw data will be stored at the bioanalytical site. If the anti-HBM 9161 antibodies can be detected, the ADA titers will be further tested and further characterized using the validated cell-based NAb assays, if necessary, based on the ADA positive rate and titers.

j. Platelet autoantibodies, including anti-GPIb/IIIa, anti-GPIb/IX and anti-GPIa/IIa antibodies, will be detected by the monoclonal antibody-specific immobilization of platelet antigen (MAIPA) or enzyme-linked immunosorbent assay (ELISA) methods. From the start of the first dose of the additional cycles, the subsequent sampling will be performed according to the blood collection schedule from Day 0 (Visit 2) on the study schedule.

k. The PK blood sample collection will be flexible and should be taken only within the time window. The blood samples will be collected within 2 h before dosing on Days 0, 7, 14 and 21, as close as possible to the time of dosing. The PK sampling can still be performed if the subject has taken the study drug before the blood collection, and the actual time of administration, dose and blood collection time need to be accurately recorded. The samples should be collected at site for follow-up visits on Day 28, 35 and 49, and the blood collection time needs to be accurately recorded. When an event of special interest (e.g., serious adverse event, etc.) occurs on and before Day 49, the investigator may choose to collect an unscheduled PK sample for the exploratory dose-response analysis, when available. If the subject withdraws from the study on or before Day 49, a PK sample may also be collected for the exploratory dose-response analysis. The PK blood samples may be collected as described above for subjects who receive the additional treatment cycles.

I. During the 21-week follow-up period, for the subjects who receive additional treatment cycles, the subsequent visits after the first dose of additional cycles should be performed same as the visits from Day 0 (Visit 2) as specified in the study schedule. Except for randomization, all the procedures will be consistent. However, the visit assessments will be performed same as with Visit 20 in the study schedule. If the Week 24 visit is less than 5 weeks from the last dose of study drug, or the last treatment cycle has not been completed at the Week 24 visit, the follow-up period will be extended to 5 weeks after the last study dose. For the subjects with extended follow-up period, the last visit assessments will also be performed same as Visit 20 in the study schedule (see Flow Chart of Additional Treatment Cycles).

m. If the assessment has been performed within  $\leq$  7 days before, it may not be performed at that visit day.

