#### Study Objectives:

Phase 2: Dose Selection and Efficacy Ev	valuation
Study Objectives:	Study Endpoints:
Primary Objectives	Primary Endpoints
- To evaluate the early efficacy of weekly subcutaneous HBM9161 340 mg and 680 mg treatment in patients with primary immune thrombocytopenia (ITP) to make a go/no go decision for the phase 3 part and select a dose to be further	
 
Proportion of subjects who achieve a response (R) during the period from Week 1 to Week 7.
 

studied in the phase 3 part, the the phase 3 part decision is go.	
Secondary Objectives	Secondary Endpoints

 
To assess the efficacy of weekly subcutaneous HBM9161 340 mg and 680 mg in patients with primary immune thrombocytopenia (ITP).
 
	
 
Proportion of subjects whose platelet count is ≥ 30 × 10^9/L and at least 2 times of baseline at 4 or more visits out of the 6 visits in the period of Week 19 through Week 24, and who had no bleeding events and no rescue treatment prior to those platelet counts
 

	
 
Proportion of subjects who achieve response (R) within 24 weeks
 

	
 
Proportion of subjects who achieve complete response (CR) within 7 weeks
 

	
 
Proportion of subjects who achieve complete response (CR) within 24 weeks
 

	
 
Proportion of subjects who achieve platelet count ≥ 50 × 10^9/L at least 2 times within 7 weeks
 

	
 
Proportion of subjects who achieve platelet counts ≥ 50 × 10^9/L at least 2 times within 24 weeks
 

	
 
Time to Response: time from imitation of treatment to first response (R) or complete response (CR)
 

	
 
Duration of response: time from response (R) or complete response (CR) to first unmet response (R) or complete response (CR)
 

	Note:
	- Reaction (R) is defined as:
	Platelet counts ≥ 30 × 10  /L and at least 2 times of baseline, confirmed by 2 tests (at least 7 days apart) , and no prior bleeding events and no rescue treatment.
	- Complete response (CR) is defined
	as: platelet counts ≥ 100 × 10  /L should be achieved and confirmed in at least 2 tests (at least 7 days apart) without prior bleeding events and no rescue treatment.

Safety Objective	Safety Endpoints

 
To assess the safety of weekly subcutaneous HBM9161 340 mg and 680 mg in ITP patients
 
	
 
Severity and incidence of adverse events during 24 Weeks
 

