#### Study Duration (for both phase 2 and phase 3 parts):

26 weeks in total (2-week screening + 3-week treatment + 21-week follow-up).

During the 21-week follow-up period, for subjects who receive additional treatment cycles, the subsequent visits after the first dose of additional cycles should be performed same as the visits from Day 0 (Visit 2) as specified in the study schedule. Except for randomization, all the procedures should be done. However, assessments to be performed should accord toVisit 20 in the study schedule. If the Week 24 visit is less than 5 weeks from the last dose of study drug, or the last treatment cycle has not been completed at the Week 24 visit, the follow-up period will be extended up to 5 weeks after the last study dose. For those subjects with extended follow-up period, the last visit assessments will also be performed as according to Visit 20 in the study schedule (see Flow Chart of Additional Treatment Cycles).

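### Subjects who withdraw within about 5 weeks of a dose have no scheduled safety contact after the 2-day withdrawal visit, apart from injection-site observation

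*Combined protocol and SAP*

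**What the plan says.** Three rules bear on how long a dosed subject is observed.

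- **Early withdrawal** (Study Schedule, note b): "the withdrawal visit should be completed within 2 days of the decision to withdraw from the study". For withdrawal in the middle of treatment the note adds: "please observe the injection site reaction at the withdrawal visit until the reaction disappears". It names no other observation after that visit.
- **Extension near Week 24** (Study Schedule, the note on additional treatment cycles between notes k and m): "If the Week 24 visit is less than 5 weeks from the last dose of study drug", or if the last cycle is still unfinished at Week 24, "the follow-up period will be extended to 5 weeks after the last study dose". The synopsis, under Study Duration, has the same trigger but says "the follow-up period will be extended up to 5 weeks after the last study dose".
- **Safety endpoint** (Study Objectives, Phase 2; Phase 3 is worded alike): "Severity and incidence of adverse events during 24 Weeks".

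The available text sets no safety contact after the withdrawal visit and does not describe what happens to a subject who stops injections but remains in the study.

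**The concern.** The clock for the withdrawal visit starts at the decision to leave, not at the last dose. A subject who decides to leave on or just after a dosing day can therefore make the last scheduled visit only days after receiving study drug. The plan does not let a subject who stays in the study, and whose last cycle ends near Week 24, finish so soon after a dose.

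The plan itself treats the weeks after dosing as relevant. The Phase 2 primary endpoint runs to Week 7, PK samples are taken to Day 49, and women of childbearing potential must use contraception until 90 days after the last dose. The Rationale describes a product that removes IgG, and low IgG at screening is an exclusion. An infection, bleed or laboratory change some weeks after a dose is an event the safety analysis should be able to capture.

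Phase 2 safety data also feed the decision to start Phase 3 and the choice of dose. With 12 subjects per arm, one unrecorded event shifts an arm's incidence by 1/12 = 8.3 percentage points.

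**Working it through.** **Inputs**
- Doses in one cycle: Days 0, 7, 14 and 21, from the PK sampling note ("within 2 h before dosing on Days 0, 7, 14 and 21").
- Planned duration: "26 weeks in total (2-week screening + 3-week treatment + 21-week follow-up" (Study Duration).
- Withdrawal visit: at most 2 days after the decision (note b).
- Extension mark: 5 weeks = 5 × 7 = 35 days after the last dose.
- Gap between cycles: at least 4 weeks = 28 days from the last dose of one cycle to the first dose of the next (Treatment Duration).

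**Plan's own figure.** 2 + 3 + 21 = 26 weeks, as stated. Week 24 is Day 24 × 7 = 168. A one-cycle completer is observed for 168 − 21 = 147 days after the last dose. On timing, the extension applies only when the last dose falls after Day 168 − 35 = 133, so in practice it concerns re-treated subjects who stay in the study.

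**Shortfall for an early leaver.** With last dose on day L, decision on day D and the visit on the last permitted day:

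shortfall = max(0, 35 − (D + 2 − L))

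It is above zero only if D − L < 33. A visit earlier in the 2-day window adds up to 2 days. For L = 21:

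| Decision day | Visit by day | Days after last dose | Shortfall against 35 days |
|---|---|---|---|
| 21 | 23 | 2 | 33 |
| 28 | 30 | 9 | 26 |
| 35 | 37 | 16 | 19 |
| 42 | 44 | 23 | 12 |
| 49 | 51 | 30 | 5 |
| 54 | 56 | 35 | 0 |
| 70 | 72 | 51 | 0 |
| 140 | 142 | 121 | 0 |

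A decision on the day of any other dose gives the same 35 − 2 = 33 days.

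**Additional cycles.** With the shortest permitted gaps, cycles start on Days 0, 49 and 98, because each start is the previous start + 21 + 28. Last doses fall on Days 21, 70 and 119, and the 35-day marks on Days 56, 105 and 154. The gap closes for decisions from Days 54, 103 and 152 (L + 33), and it reopens with each new cycle.

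**Number affected.** The documents give no dropout rate. Phase 2 allows replacement of up to 6 dropouts through Week 7 against 36 planned subjects (6/36 = 16.7%), but that is a cap, not an expected rate. For scale only, assume that 5% to 15% of the 230 Phase 3 subjects left inside the window. That would be 11.5 to 34.5, or about 12 to 35 subjects. Nothing in the documents supports that range.

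**The case against.** The strongest reply is that this argues from silence in an incomplete text. The available document is a synopsis with a schedule. It has no adverse-event reporting section and no section on discontinuation, and the adverse-event row of the schedule is blank as extracted. Note b fixes when a visit takes place; it does not say that adverse-event collection ends there. This stands. A reader might infer that late adverse events in early leavers are never collected. The documents support only the narrower statement that the available text schedules no such collection, with injection-site reactions as the exception.

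Second, the 5 weeks is a scheduling rule for subjects still in the study. It is nowhere called a safety minimum, and the Study Duration wording can be read as a ceiling. This also stands. The 35 days serve here as the plan's own benchmark, not as a general requirement, and the two wordings need reconciling in any case.

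Third, most of the follow-up period is unaffected. A subject who leaves at Day 70 after one cycle may be seen 51 days after the last dose. The point is therefore confined to decisions made less than 33 days after a dose.

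Fourth, a reader might infer that subjects who only stop injections are handled under note b. The note applies to withdrawal from the study; on stopping injections alone the text is silent. For true withdrawal, later contact depends on the subject's agreement.

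Finally, a reader might conclude that the safety comparison between arms is biased. Unequal follow-up could produce that, but the documents give no rate or direction by arm. One contact at 5 weeks would also leave early leavers short of the 24-week window.

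None of this removes the core: followed as written, note b can leave a recently dosed subject with only days of scheduled safety observation.

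**Conclusion.** The point holds for subjects who decide to withdraw less than 33 days after their last dose, which means before Day 54 for one full cycle. Their scheduled post-dose safety observation falls short of the 35-day mark by up to 33 days, with the visit at the end of its window. The shortfall shrinks day by day as the decision comes later, and it can recur after each additional cycle. Adverse events in these subjects may be under-counted against the 24-week safety endpoint.

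This rests on the text available; if an adverse-event section elsewhere already sets a post-dose collection period, note b need only refer to it. The number of subjects affected and any imbalance between arms are unknown. It is a worthwhile, inexpensive improvement to data collection and does not show that the safety comparison is invalid.

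**What to change.** 1. Keep the 2-day withdrawal visit. Add to note b and to Study Duration one further contact at 5 weeks after the last study dose for subjects who withdraw before that mark, by telephone if no visit is possible and unless the subject refuses contact. Collect adverse events, bleeding, and concomitant or rescue treatment.
2. Reconcile the Study Duration wording of the 5-week extension with that in the Study Schedule note, so that the length of follow-up is unambiguous.
3. State that note b applies to withdrawal from the study, and that subjects who only stop injections stay on the visit schedule for data collection.

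The cost is protocol wording and about one call per affected subject. Some contacts will fail, and the reported adverse event incidence may rise slightly. The contact reduces truncation against the 24-week window but does not remove it.
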